Clinical Investigation Plan

CP321

Investigation of a supporting ostomy product intended for leakage detection

April 2021- June 2022

CHANGE LOG

VER-SION NUMBER	ISSUED BY (INITIALS)	COMMENTS (MAJOR CHANGES SINCE LAST REVISION)
1.0	██████	First approved version
2.0	██████	Front page+p.15: Timeline changes from start February to start April P 17 added: In the Coloplast database potential subjects are identified by the following search criteria: subjects who have consented to be contacted for future clinical investigations, has ileostomy or colostomy and be at least 18 years of age.

This confidential document is the property of Coloplast A/S.
No unpublished information contained herein may be
disclosed without written approval of Coloplast A/S.

SYNOPSIS OF THE CLINICAL INVESTIGATION

The aim of the study is to investigate the performance of a new supporting ostomy product. The intended purpose of the test product is to detect leakage beneath the ostomy baseplate and inform the user about this through a notification given on a smartphone handed out to subjects.

Title: Investigation of a supporting ostomy product intended for leakage detection

Test products and comparator

The test product consists of the following:

- Adhesive Sensor Layer
- A Transmitter which is connected to the Sensor Layer
- An app (Installed on a smartphone handed out to the subjects) The app is communicating sensor status to the user
- Charger to the transmitter
- Cable to the charger

No comparator is used in this study

Intended purpose: The sensor layer system is intended to be used together with an ostomy baseplate and bag, to detect and notify user of the occurrence of output leakage under an ostomy baseplate

Objective(s)

The primary objective is:

- The primary objective is to evaluate the system performance of the test product

Secondary objectives are:

- To evaluate reliability of notifications
- To evaluate user experience to support commercial claims
- To explore quality of life

Design of the investigation

Single arm design. Open-labelled

Study duration: 21 days + 3 days.

Study visits will be conducted remotely via video calls/phone calls if technically possible. If considered necessary by the study nurse, the visits can take place either in subjects own home or at a test facility at Coloplast.

V0: Inclusion

V1: Baseline demographics & evaluation (questionnaire) & Introduction to test product, start test period

V2: Termination

Vx: Follow up visits if needed

Primary endpoint and secondary endpoint(s)

Primary endpoint:

- The primary endpoint is to evaluate system performance focusing on accuracy of data classification into true positive and true negative

Secondary endpoints:

- Frequency of leakage onto clothes before and after use of test product
- Experience of leakage onto clothes compared to only using usual product
- Reliability of notifications
- Ability to move with test product
- Subjects worry of leakage before and after use of test product
- Confidence to avoid full leakage with test product compared to only using usual product
- Confidence in daily life compared to only using usual product
- Feeling of control with test product compared to only using usual product
- Control of leakage progression with test product compared to only using usual product
- Feeling of security with test product compared to only using usual product
- Evaluation of confidence to increase social activities with test product compared to only using usual product
- Evaluation of sleep with test product compared to only using usual product
- Confidence at night with test product compared to only using usual product
- Evaluation of users' preference
- Reason for preference
- Evaluation of users' peace of mind with test product
- To evaluate users' assessment of QoL with test product compared to usual product
- Adhesive residue to transmitter
- Adhesive residue to skin

Population/subjects

We will include n=25 subjects as a minimum of 25 subjects are needed to evaluate sensor performance and to have a potential support of relevant core claims.

N=15 subjects will get the test product app on an Android phone and n=10 users will get the test product app on an Iphone.

We strive to include an equally number of subjects in the categories 1pc, 2pc.

Subjects may use any Coloplast baseplate (Assura, SenSura, SenSura Mio) flat, convex and concave
Up to 5 subjects may use a mouldable ring (see exclusion criteria)

Inclusion criteria:

1. Have given written informed consent
2. Be at least 18 years of age and have full legal capacity
3. Have had a stoma for more than three months
4. Have intact skin on the area used in the evaluation meaning no broken skin and only minor discolouration of the skin (assessed by investigator)
5. Be able to use one of the five sensor layer sizes (i.e. Ø40, Ø50, Ø60, Ø70, Ø80 mm)
6. Ileo- or colostomists with liquid output (Bristol scale type 6-7).
7. Currently using a Coloplast product (1pc/2pc Flat/Convex/Concave) from e.g Assura/SenSura/SenSura Mio
8. Have self-reported problems with leakage* (three times within 14 days)
9. Have worry of leakage 'to some, high or very high degree'
10. Is familiar with the use of a smartphone

*Leakage: Leakage is defined as output from the stoma on the backside of the baseplate (underneath the baseplate)

Subjects who uses a mouldable ring may be included, if able to fit one of the five test products while wearing the ring. The sensor layer should be applied to the peristomal skin, not covering the ring.

Exclusion criteria

1. Currently receiving or have within the past 2 month received radio- and/or chemotherapy
2. Currently receiving or have within the past month received topical steroid treatment in the peristomal skin area or systemic steroid (tablet/injection) treatment.
3. Are pregnant or breastfeeding
4. Participating in other interventional clinical investigations or have previously participated in this investigation. Exception: Participation in other Coloplast sponsored clinical investigations is accepted under the circumstances that the subject has paused the activities in the investigation and are otherwise complying with the inclusion and exclusion criteria of this protocol.
5. Known sensitivity towards test product
6. Known sensitivity towards acrylate
7. Is using/have a pacemaker
8. Is using ostomy paste or ostomy powder

LIST OF ABBREVIATIONS

ABBREVIATION	WRITTEN OUT	EXPLANATION
ADE	Adverse Device Effect	See section 18.2
AE	Adverse Event	See section 18.1
ASADE	Anticipated Serious Adverse Device Effect	See section 18.4
CIP	Clinical Investigation Plan	
CRF	Case Report Form (paper or electronic)	Questionnaire to be used for data collection
CM	Clinical Manager	
DQF	Data Query Forms	A DQF is a query specifically used in clinical research. The DQF is the primary data query tool from the sponsor to clarify discrepancies and ask the investigator for clarification. The DQF is part of the data validation process in a clinical investigation.
DD	Device deficiency	
EC	Ethics Committee	
IB	Investigator's Brochure	Compilation of the current clinical and non-clinical information on the investigational medical device(s,) relevant to the clinical investigation.
IFU	Instruction For Use	
ITT	Intention to Treat	

1.2. Investigators

The CM is responsible for maintaining an updated list of all PIs, investigation sites and institutions.

PRINCIPAL INVESTIGATOR

2. Rational/justification for conducting the clinical investigation

[figure not shown]
People with intestinal stomas (especially an ileostomy) can have, despite development of better ostomy products, problems with leakage which influence their quality of life negatively [1,2].

To overcome this, Coloplast has developed a new supporting ostomy product, which has an adhesive sensor layer that should be place underneath the baseplate. The sensor layer consists of an electronic sensor system, that continuously detects moisture and output leakage underneath the baseplate. A transmitter connected to the sensor layer continuously evaluate the incoming information and sends a status to a

smartphone software application, which based on a predefined flow decides which information to deliver to the user about the baseplate status.

The purpose of this study is to investigate the sensor performance of this new supporting product with a test product app that is either used from an iPhone or an Android (Samsung) phone. The target population in this investigation is subjects with either an ileostomy or colostomy, who have liquid output and self-reported problems with leakage. Based on the results obtained in this study, new and better ostomy devices that can help detect leakage can be developed.

Two previous exploratory studies have been conducted (CP278 and CP308) [3+4]. In the first study (CP278) it was shown that the sensor technology worked, [REDACTED] The [REDACTED]

Based on the results obtained in the present investigation, new and better ostomy devices can be developed that help improving the users confidence and HRQoL.

3. Objective(s) and hypotheses of the clinical investigation

3.1. Objective (s)

The primary objective is:

- The primary objective is to evaluate the system performance of the test product

Secondary objectives are:

- To evaluate reliability of notifications
- To evaluate user experience to support commercial claims
- To explore quality of life

The study is conducted as an exploratory study with no formal hypotheses.

4. Investigational device and comparator(s)

Subjects will test the test product for 21+3 days. The test product is used in combination with the ostomy baseplates usually used by the subject. Subjects will be supplied with a sufficient number of test products (sensor layers) to support their normal change routine.

4.1. Description of investigational device

The investigational device consists of the following:

- Adhesive patch - sensor layer
- Transmitter
- Sensor app (Installed on the smartphone handed out to the subjects). The app is communicating sensor status to the subject
- Charger to the transmitter

[figure not shown]
[figure not shown]

Figure 1: Investigational device

Subjects will be provided the device including a spare transmitter and sufficient number of adhesive sensor layers

The following sensor layer sizes will be available in the study: ø40, ø50, ø60, ø70 and ø80, referring to the inside diameter of the sensor layer. The study nurse and subject will together find the right size of sensor layer that best fit the subject.

4.1.1. Manufacturing

Coloplast A/S, [name], is the manufacturer of the non-CE marked Investigational Product.

4.2. Identification and traceability of the device

The investigational test device will be identified as CP321/1

Investigational device label Ref [9] can be found in IB [11]

4.3. Intended purpose of the device in the clinical investigation

Intended purpose of device:

The sensor layer system is intended to be used together with an ostomy baseplate and bag, to detect and notify user of the occurrence of output leakage under an ostomy baseplate.

Intended medical indication(s):

The product is indicated for users with an ostomy, mainly ileostomy and colostomy with liquid output.

The product is to be used on intact skin.

Intended mode of action:

The sensor layer is applied under an ostomy baseplate that is then attached to an intact peristomal skin around the stoma. The sensor layer detects occurrence of output leakage under the ostomy baseplate and the user is notified of the leakage via a smartphone software application.

Application:

In the Instruction for Use (IFU), application, few warnings, cautions and pre-caution of how to use test product are given. See IFU in Investigators Brochure (IB) [11]

4.4. Intended population for the device

Subjects with ileostomy or colostomy with liquid output are the intended population for this device.

4.5. Handling of the investigational device

The handling of the test products is described in details in the Instruction for Use (IFU), which is included in all boxes with test products. Storage conditions are also stated in the IFU.

All Investigators / investigator representatives will receive training by sponsor / investigator in the handling and correct use of the test products. The Investigator/investigator representative will train the subjects in the correct use of the test products

4.6. Total number of devices intended for the clinical investigation

Subjects will be delivered one test product per day and 6 extras. Subjects will be delivered a starter box and retail boxes with sensor layers (10 in a box)

Each subject will be supplied with test products and study supplies as described below:

- 1 phone (iPhone or Android) with a specially designed application installed
- 1 charger
- 1 charging cable
- 1 charging adapter
- Two transmitters
- Test products to support a daily change pattern + 6 extra
- One iPhone for the Clinical Trial App

4.7. Description of the comparator product(s)

No comparator is used in this study.

[figure not shown]
5. Design of the clinical investigation

5.1. General

An open-labelled, single arm study design was chosen for this study.

Study duration: 21 days + 3 days.

Study visits will be conducted remotely via video calls/phone calls if technical possible. If considered necessary by the study nurse, the visits can take place either in subjects own home or at a test facility at Coloplast.

V0: Inclusion

V1: Baseline demographics & evaluation (questionnaire) & Introduction to test product, start test period.

V2: Termination

Vx: Follow up visits if needed

21 days are considered sufficient to meet endpoints of performance of the sensor layer, user experience with test product and to observe trends in changes of quality of life. The visit window of 3 days is chosen for flexibility purposes.

5.2. Primary endpoint

- The primary endpoint is to evaluate system performance focusing on accuracy of data classification into true positive and true negative

5.3. Secondary endpoints

Secondary endpoints:

- Frequency of leakage onto clothes before and after use of test product
- Experience of leakage onto clothes compared to only using usual product
- Reliability of notifications
- Ability to move with test product
- Subjects worry of leakage before and after use of test product
- Confidence to avoid full leakage with test product compared to only using usual product
- Confidence in daily life compared to only using usual product
- Feeling of control with test product compared to only using usual product
- Control of leakage progression with test product compared to only using usual product
- Feeling of security with test product compared to only using usual product
- Evaluation of confidence to increase social activities with test product compared to only using usual product
- Evaluation of sleep with test product compared to only using usual product
- Confidence at night with test product compared to only using usual product
- Evaluation of users' preference
- Reason for preference
- Evaluation of users' peace of mind with test product
- To evaluate users' assessment of QoL with test product compared to usual product
- Adhesive residue to transmitter

- Adhesive residue to skin

Explorative endpoints:

- Change in HRQoL, Appendix 1
- Change in Ostomy Leakage Impact (OLI), Appendix 2
- Evaluation of self-management (predictability of change) of stoma appliance compared to usual product

5.4. Rationale for selection and measurement of endpoints

The endpoint of system performance has been selected as primary endpoint in this investigation as this is the core performance measure of the system. The objective measure of leak notification accuracy (system performance) will be obtained by comparing leak areas from pictures of the backside of the adhesive baseplate to the output leak notifications received by the subjects for each of the leak sensor areas.

Secondary endpoints are related to users experience of reliability of leak notifications as well as users experience of what the product might offer them to support control, confidence and feeling of security in everyday life and whether it may help to reduce their worry of leakage, especially leakage onto clothes.

Secondary endpoints related to user experience with use of test product are asked on five-point Likert scales or as yes/no questions.

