6.1.1. Inclusion criteria

Inclusion criteria:	Inclusion:

1. Have given written informed consent
 
2. Be at least 18 years of age and have full legal capacity
 
3. Have had a stoma for more than three months
 
4. Have intact skin on the area used in the evaluation meaning no broken skin and only minor discoloration of the skin (assessed by investigator)
 
5. Be able to use one of the five test products (i.e. Ø40, Ø50, Ø60, Ø70, Ø80 mm)
 
6. Ileo- or colostomists with liquid output (Bristol scale type 6-7).
 
7. Currently using a Coloplast product (1pc/2pc Flat/Convex/Concave) from e.g Assura/Sen-Sura/SenSura Mio
 
8. Have self-reported problems with leakage* (three times within 14 days)
 
9. Have worry of leakage 'to some, high or very high degree'
 
10. Is familiar with the use of a smartphone
 
*Leakage: Leakage is defined as output from the stoma on the backside of the baseplate (underneath the baseplate)
	
1. To meet the Helsinki Declaration
 
2. To meet the Helsinki Declaration
 
3. Recovered from ostomy surgery
 
4. The skin must be intact, otherwise the product will change classification category.
 
5. The technical design of the device requires use of one of the five sizes
 
6. The technical design of the device requires liquid output
 
7. To minimize unknown factors from competitor adhesives, only users of Coloplast products can be enrolled in this study.
 
8. The sensors in the product will only be activated by moist/leakage so in order to be able to evaluate the product the subjects need to have a certain amount of leakage.
 
9. Users who do not worry of leakage at any or low degree are excluded.
 
10. Users who do not know how to maneuver a smartphone will have to large difficulties in using the product and will also not be able to use the product going forward as it requires that the user has a smartphone.

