** Besides a negative pregnancy test the women must also commit to use safe contraceptives during the study period (i.e. contraceptive coil, hormone base contraceptives or surgical sterilisation). However, in some cases when the women are older than 50 years, but are not yet post-menopausal, the investigator may evaluate that it is not reasonable to ask these women to start using safe contraceptives for the duration of the investigation (e.g. if the subject is abstinent, the partner is surgically sterilised, or either subject or partner is infertile). In these cases, the investigator can include the woman, but has a responsibility of ensuring that he/she has done what he/she can to prevent these subjects from becoming pregnant. As a minimum investigator must talk to the women about the risk of and how to avoid unwanted pregnancy at inclusion and at every visit hereafter.

Subjects who uses a mouldable ring may be included, if able to fit one of the five test products while wearing the ring. The sensor layer should be applied to the peristomal skin, not covering the ring.

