7.2. Flow-chart

Table 1 chart showing the connection between visits and assessments.

	Registration/measurement	PERFORMED BY	INFOR-MATION MEETING	SCREEN-ING	VISIT 1	VISIT 2 TERMI-NA-TION	CON-TINUOUS LY
	General						
	Oral information	Investigator	X				
	Written informed consent	Investigator	X	X			
	Check of in- and exclusion criteria	Investigator		X			
	Insurance of subjects' wellbeing and compliance with CIP	Investigator		X	X		
	Registration of Demographics/assessments						
	
 • Gender • Age • Weight • Height • Duration of ileostomy/colostomy (year when created) • Reason for creation of the stoma • Shape of the stoma • Size of the stoma (diameter on widest place and height) • Body profile • Physical activity • Sweat • Output • Information about the current stoma product • Normal changing pattern • Normal main reason for change of product • Stoma awareness • Technical ability • Use of accessories 	Investigator			X		
	
 ○ Wear time ○ Reason for change 	Subject					X X

No.	Registration/measurement	PERFORMED BY	INFOR-MATION MEETING	SCREEN-ING	VISIT 1	VISIT 2 TERMI-NATION	CONTINUOUS LY
	Primary endpoint						
1	To evaluate system performance focusing on accuracy of data classification into true positive and true negative	sponsor representa-tive (evaluate pic-tures, assess leak to sensors) Subject (takes pic-tures at each change)					X
	Secondary endpoint(s)						
2	Frequency of leakage onto clothes	Subject			X	X	
3	Overall experience of leakage onto clothes with test product compared to only using usual product	Subject				X	
4	Reliability of notifications	Subject				X	
5	Ability to move with test product	Subject				X	
6	Subjects worry of leakage	Subject			X	X	
7	Confidence to avoid leakage onto clothes with test product compared to only using usual product	Subject				X	
8	Confidence in daily life compared to only us-ing usual product	Subject				X	
9	Feeling of control with test product com-pared to only using usual product	Subject				X	
10	Control of leakage progression with test product compared to only using usual prod-uct	Subject				X	
11	Feeling of security with test product com-pared to only using usual product	Subject				X	
12	Evaluation of confidence to increase social activities with test product compared to only using usual product	Subject				X	
13	Evaluation of sleep with test product com-pared to only using usual product	Subject				X	

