10.1. Statistical design, method and analytical procedures

Definition of analysis populations

Intention to Treat (ITT) and Safety populations will be defined at a formal data review meeting just before database lock. As a minimum, the data manager, the clinical manager and the statistician will be involved in the classification of subjects.

The ITT population (full analysis set) will be constituted by all included subjects who:

- Have provided valid informed consent
- Have information for at least one of the endpoints

The Safety population will constitute by subjects who have given informed consent.

All statistical analysis and summaries will be based upon the ITT population whereas adverse events and Device deficiencies will be assessed based on the safety population. Invalid individual data points may be omitted from analysis even though the corresponding subject is part of the ITT population. Any exclusion of data points will be documented.

A formal PP population is not planned due to the explorative nature of the investigation. Considering the data obtained it might however be considered to make additional explorative analyses based on a subset of the ITT population.

Analysis of endpoints, individual questions and baseline data

All endpoints and individual questions as well as baseline/demographic data will be listed and summarized by descriptive statistics. Summaries can be made for 1- and 2-piece users as well as for the subgroups (flat, convex and if relevant concave) or (iPhones, Androids), if relevant.

The accuracy of the sensor performance will be calculated based on picture data used to correlate notifications given with output to sensors on baseplates (primary endpoint). The accuracy will be calculated by dividing the true positive plus the true negative with the total sum of the true positive, true negative, false positive and false negative.

For secondary endpoints where the possible answer is Yes or No, the proportion of subjects answering "Yes" will be calculated. By use of an exact test in the Binomial distribution a 95% confidence interval will be estimated for the proportion. Further, it will be tested if the proportion is significantly different from 50% when using a 5% test level. For questions answered on a 5-point scale the answers can be grouped in 2 (e.g. "higher" or "much higher" against the rest of the answers) and analyzed by the above described method.

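### One pooled accuracy per sensor area, with output on the sensors as reference, leaves missed leaks and false alarms per wear without a planned measure

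*Combined protocol and SAP*

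**What the plan says.** **Unit and reference in section 5.4.** System performance is obtained by "comparing leak areas from pictures of the backside of the adhesive baseplate" with the "output leak notifications received by the subjects for each of the leak sensor areas".

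**Reference in sections 10.1 and 7.2.** Section 10.1 describes "picture data used to correlate notifications given with output to sensors on baseplates (primary endpoint". The flow-chart has a sponsor representative evaluate the pictures and "assess leak to sensors".

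**Metric.** Section 10.1 gives one figure: true positives plus true negatives, divided by the sum of all four cells. It defines neither the cells nor the unit counted. No sensitivity, specificity or false-alarm rate is specified. Appendix 4 adds only the subject's own rating of how reliable the notifications were.

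**What the device is for.** Section 4.3 states the purpose as "to detect and notify user of the occurrence of output leakage under an ostomy baseplate". In section 6.1.1, "Leakage is defined as output from the stoma on the backside of the baseplate (underneath the baseplate"; contact with a sensor is not required.

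**Coverage.** For mouldable-ring users (up to 5 subjects, according to the synopsis), "The sensor layer should be applied to the peristomal skin, not covering the ring".

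**The concern.** The planned figure asks whether a wet sensor area signals and a dry one stays silent. The user needs to know whether the baseplate leaks and whether a notification can be trusted. The two questions can have different answers for three reasons.

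- A leak may wet only a few of the areas, and many wears have no leak. Dry areas then dominate the denominator, and an overall accuracy mostly reflects them.
- One falsely alarmed area costs one reading out of many, but the user experiences it as a false alarm for that wear.
- A leak that reaches no sensor has no clear place in the table. If output on the sensors is the reference, every area in that wear is dry, and with no notification every area is scored as correct.

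Section 5.4 calls this the core performance measure, and section 10.4 allows results to be used for claims. A high accuracy could therefore be quoted as leak detection when it does not measure that.

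**Working it through.** The plan states no accuracy target, power or sample size calculation, so there is no figure to reproduce. What follows is an illustration by expected counts.

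**Inputs from the documents**
- 25 subjects (section 6) and 21 days (section 5.1). Supply is one sensor layer a day plus spares (section 4.6). At daily change, 25 × 21 = 525 wears. This is a supply allowance, not a forecast of use.
- Inclusion criterion 8, three leaks in 14 days: 3/14 × 21 × 25 = 112.5, taken as 112 leaking wears. Dry wears: 525 − 112 = 413.

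**Assumed, because the documents do not say**
- 8 sensor areas, and 2 wet areas for a leak that reaches the sensors.
- Area sensitivity 95%; area specificity 98%, with 99.5% as an alternative.
- Independent areas.
- A share *u* of leaks reaching no sensor, from 0 to 30%.

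**1. A device that never notifies (u = 0).** Area readings: 525 × 8 = 4,200. Wet: 112 × 2 = 224. All 4,200 − 224 = 3,976 dry readings are correct, so accuracy = 3,976/4,200 = 94.7%. Sensitivity per leaking wear is 0 of 112.

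**2. False alarms per dry wear.** The formula is 1 − specificity^k, for k areas.

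| Area specificity | 4 areas | 8 areas | 12 areas |
|---|---|---|---|
| 98% | 7.8% | 14.9% | 21.5% |
| 99.5% | 2.0% | 3.9% | 5.8% |

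With 8 areas and 98%, that is 0.149 × 413, or about 62 dry wears.

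**3. Leaks that reach no sensor, if output on the sensors is the reference.**
- Area accuracy = [224(1−u) × 0.95 + (4,200 − 224(1−u)) × 0.98] / 4,200
- Leaking wears detected by a wet area = (1−u)(1 − 0.05²)
- Leaking wears with any notification, chance alarms included = (1−u)(1 − 0.05² × 0.98⁶) + u(1 − 0.98⁸)

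| u | Area accuracy | Detected by a wet area | Any notification |
|---|---|---|---|
| 0 | 97.84% | 99.75% | 99.8% |
| 10% | 97.86% | 89.8% | 91.3% |
| 20% | 97.87% | 79.8% | 82.8% |
| 30% | 97.89% | 69.8% | 74.3% |

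Area accuracy does not fall as more leaks are missed; it rises slightly. The last two columns differ because a false alarm from a dry area is credited as a detection if any notification counts.

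**4. Where the gap closes.** With one area per baseplate and no off-sensor leaks, area and wear are the same unit and the two accuracies coincide. For a silent device with one wet area per leak, accuracy is 1 − 3/14 = 78.6% with one area and 1 − (3/14)/4 = 94.6% with four. The size of the gap depends on inputs that the documents do not give.

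**The case against.** **A reader might infer that the plan scores off-sensor leaks as true negatives.** No rule says so. It is the natural reading of section 10.1 and the flow-chart. But section 5.4 starts from leak areas on a picture of the whole back of the baseplate, which could allow such a leak to be scored as a miss. Section 10.1 does not name a counting unit either; scoring by area rests on section 5.4. What stands is an unresolved difference between the two sections.

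**A reader might infer from the layer sizes that much of the baseplate is not sensed.** The sizes are given as "referring to the inside diameter of the sensor layer", which describes the opening. Baseplate dimensions, stoma opening and sensor layout are not in the text, and the size is chosen to fit the subject. Only the mouldable-ring instruction makes off-sensor leaks plausible, and it concerns at most 5 of 25 subjects. The 0 to 30% range in the working has no basis in the documents.

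**A reader might say that false alarms are hidden.** They are not: false positives lower accuracy, section 10.1 permits further summaries, and at each change subjects can give a notification or leakage under the baseplate as the reason. What is missing is a prespecified rate per wear. If readers record only leak to sensors, later summaries could not recover off-sensor leaks without a second reading of the photos.

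**The study is exploratory**, with no hypotheses, power or success criteria, and area accuracy is a legitimate technical answer to the stated objective. The leakage definition is a footnote to an inclusion criterion, not an endpoint reference standard. This argues against replacing the primary endpoint, and making the wear-level result the headline would be a preference. It does not answer the mismatch with the intended purpose in section 4.3.

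**Conclusion.** The point holds as a should-fix, with moderate confidence. The reference in section 5.4 and that in section 10.1 and the flow-chart need reconciling, the four cells and the unit are undefined, and pooled area accuracy alone cannot show how often leaks are missed or how often a dry wear carries a false alarm. On the assumed inputs a silent device reaches 94.7%, and false alarms affect about 15% of dry wears at 98% area specificity or about 4% at 99.5%. These figures rest on 8 independent areas, 2 wet areas per leak and daily changes. The dilution by dry areas needs only more than one area per baseplate; the problem of unsensed leaks also needs leaks that bypass every sensor, and their frequency is unknown.

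**What to change.** In sections 5.4 and 10.1:

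1. State one reference for the area-level comparison, consistent with the flow-chart. Define true and false positives and negatives, and name the unit counted.
2. Add one field to the photo reading: output anywhere on the back of the baseplate, yes or no.
3. Keep per-area accuracy. Alongside it, prespecify sensitivity per leaking wear (any output on the photo, any output leak notification during that wear) and false alarms per dry wear, with confidence intervals that allow for repeated wears within a subject.
4. List leaks that reached no sensor separately, with whether a notification occurred, so that a chance alarm elsewhere is not read as detecting them.

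The cost is protocol wording and one extra reading field. Photos are already taken at every change, so no further subjects, visits or pictures are needed. The downside is that the added figures may look less favourable than area accuracy. The field should be in place before reading starts; adding it later means reading every photo again.
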